Because of the invasive nature of the interventions, neither the trial participants nor the investigators will be blinded to group allocation.

Visual analog scale (VAS) pain intensity scores will be collected from patients at rest at 6, 12, 18, 24, 30, 36, 42, 48, and 72 hours after surgery and then once daily (at noon \pm 4 hours) through postoperative day 14. Subjects will also record an unscheduled pain score immediately before any requested opioid pain medication. The exact time of the assessment will be recorded to limit variability. Total opioid consumption in IV morphine equivalents (mg) during the first 48 hours postoperatively will be tracked for each subject.

Pain scores obtained during the opioid medication-specific window (see table below) will be replaced with the worst observation carried forward (WWOCF). For subjects who take a rescue medication, their VAS pain scores recorded within the window of controlled type of rescue medication will be replaced by the “worst” observation. The worst observation will be the highest VAS score from the end of the previous rescue window or the end of surgery, whichever is later.

Opioid Rescue Medication Window		
Medication	Route	Window Used to Impute VAS
Oxycodone, Oxycocet, Percocet, acetaminophen-oxycodone, Oxycontin	PO, IM, IV, SC	6 hours
Morphine	IV, PO, SC	4 hours
Hydromorphone (Dilaudid), Hydromorphone hydrochloride	IV	2 hours
Hydromorphone (Dilaudid), Hydromorphone hydrochloride	PO, IM, SC	4 hours
Hydrocodone	PO	6 hours
Fentanyl	IV, PO, IM	6 hours
Hydrocodone combination product - Vicodin, Norco, Lorcet, Lortab, hydrocodone-acetaminophen	PO	6 hours
Codeine combination product - Tylenol 3, acetaminophen-coedine, Paracetamol Forte, Tylenol 4	PO	6 hours
Ultram, Tramadol, Tramadol hydrochloride	PO	6 hours
PO = oral, IV = intravenous, IM = Intramuscular, SC = subcutaneous,.		
If other rescue medications not listed above are given, the window will be determined post-hoc. If a combination opioid product is given, the window will be determined by the opioid part of the medication.		

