- c. Justification and safety information if non-FDA approved drugs without an IND will be administered.

7. Study Statistics

- a. Primary outcome variables:

The study has two co-primary endpoints: (1) the mean Area under the Curve (AUC) of visual analog scale (VAS) pain intensity scores from 0 to 48 hours postoperatively and (2) total opioid consumption (IV morphine equivalents, mg) from 0 to 48 hours postoperatively. The primary hypothesis will be assessed in joint hypothesis testing which controls the type I error at 0.025 across both non-inferiority tests; AUC for VAS pain scores and total opioid consumption through 48 hours postoperatively. Significance will need to be achieved for both co-primary endpoints.

For analyzing the AUC of the VAS pain assessment, we will use an approach that has been previously used in Pacira studies. The area under the curve (AUC) is derived using the trapezoidal rule (see formula below) using the adjusted and imputed VAS pain scores. The VAS scores will be adjusted for the use of rescue medication using the WWOCF approach. AUC will start with the first postsurgical pain assessment. All pain assessments through 48 hours after surgery, including both scheduled and unscheduled will be used in deriving AUC. Exact assessment times will be used in deriving AUC.

$$AUC = \left\{ \sum_{i=2}^n (p_i + p_{(i-1)})(t_i + t_{(i-1)}) \right\} / 2$$

The AUC for VAS may be analyzed using ANOVA with treatment group as a main effect and include other covariates as deemed reasonable. Based on the model, the LS Mean and SE will be reported for each treatment group. The 95% confidence interval for the difference between

treatment groups and the one-sided test performed at 2.5% level of significance will be inspected for non-inferiority.

Total opioid consumption over 48 hours postoperatively will be abstracted by our research assistant from the medical administration record (MAR) as it appears in the EMR for each patient.

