The analysis of total opioid consumption over 48 hours is based on an approach that has been used previously in Pacira studies. For the endpoint total opioid consumption (IV morphine equivalents, mg) from 0 to 48 hours postoperatively, opioid dose will be converted to IV morphine equivalent dose using the conversion factor from the table below. The endpoint will be the summation of all opioids taken post-surgery through 48 hours. Subjects with no opioid use during the period in question will be assigned a dose of 0 mg for summaries.

The total opioid consumption through 48 may be analyzed using ANCOVA with treatment group as a main effect and include other covariates as deemed reasonable. Based on the model, the LS Mean and SE will be reported for each treatment group. The 95% confidence interval for the difference between treatment groups and the one-sided test performed at 2.5% level of significance will be inspected for non-inferiority. The data may be natural log transformed.

Medication	Unit	Route	IV Morphine Conversion Factor
Duramorph	mcg	IT	0.1
Oxycodone, Oxycocet, Percocet, acetaminophen-oxycodone	mg	PO	0.5
Morphine	mg	IV, IM, SC	1
Morphine	mg	PO	0.33
Hydromorphone (Dilaudid)	mg	IV, IM, SC	6.67
Hydromorphone (Dilaudid)	mg	PO	1.3
Fentanyl	mg	IV, PO, IM	100
Hydrocodone combination product - Vicodin, Norco, Lorcet, Lortab, hydrocodone-acetaminophen, Ketobemidone	mg	PO	0.33
Codeine combination product - Tylenol 3, acetaminophen-coedine, Paracetamol Forte, Tylenol 4	mg	PO	0.05
Ultram, Tramadol, Tramadol hydrochloride	mg	PO, IM	0.08
Demerol, Meperidine, Pethidine	mg	IV, SC	0.1
Demerol, Meperidine, Pethidine	mg	PO	0.033
Ketobemidone, Oxycodone	mg	IV	1

Regarding the non-inferiority margin for the total opioid endpoint, previous literature indicated a difference of 10.6mg IV morphine equivalent dose daily is a clinical different threshold [24]. Therefore, total opioid consumption through 48 hours for LB treatment group is to be no more than 21.2 IV (10.6 x 2 Days) morphine equivalent doses greater than the total opioid consumption through 48 for TEA treatment group. It may be reasonable to apply a natural log transformation, in which case the NIM threshold will be adjusted accordingly.

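### Rescue windows for unlisted opioids may be set after the data are in, unblinded, and the window and conversion tables do not match; this could bias the pain co-primary, though probably only slightly

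*Combined protocol and SAP*

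**What the plan says.** Section 4a (Study design) has a table of rescue windows of 2, 4 or 6 hours by drug and route. A pain score falling inside a window is replaced by the worst observation (WWOCF). The note under the table adds: "If other rescue medications not listed above are given, the window will be determined post-hoc". It names no decision-maker, deadline, default or condition of blindness.

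The same section states that "neither the trial participants nor the investigators will be blinded to group allocation", and section 4c repeats this. No blinded statistician or blinded adjudication is described.

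Section 7a (Primary outcome variables) carries the windows into the endpoint: "The VAS scores will be adjusted for the use of rescue medication using the WWOCF approach". It also says of the pain AUC and the 48-hour opioid total: "Significance will need to be achieved for both co-primary endpoints".

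Section 4a schedules an interim comparison of mean 0-48 h AUC between groups at 20 patients per group. Section 7b attaches a futility boundary to it.

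Section 7a also has a table of IV morphine conversion factors. It includes drugs absent from the window table, such as "Demerol, Meperidine, Pethidine" and the ketobemidone part of the row "Ketobemidone, Oxycodone".

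**The concern.** An imputation window is part of the definition of the endpoint. If it is chosen after the data are in, by people who know the allocation and can see the scores, the choice can follow the result. A longer window for a drug used mainly in the TEA arm would raise that arm's AUC and favour non-inferiority. A shorter window for a drug used mainly in the LB arm would do the same. Rescue use could plausibly differ by arm, since section 3 (Background) puts TEA failure as high as 30%, with many of those patients needing supplemental opioids.

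The interim adds a second difficulty. A window chosen late could follow an arm-level AUC comparison, or the interim and final analyses could use different windows.

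The opioid co-primary has a smaller gap of its own. A dose with a window but no conversion factor has no defined value in the total.

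**Working it through.** **1. The plan's own figure.** Section 7a gives 50 per arm for margin 38, SD 55, true difference 0, one-sided alpha 0.025, 90% power and a Mann-Whitney test. The normal approximation is n = 2 × [55 × (1.960 + 1.282) / 38]² = 44.0, so 45. The exact t calculation gives 46. Multiplying by π/3 for Mann-Whitney with normal data gives 48.2, so 49. Power at 50 per arm is about 0.92. The stated size is therefore in order, and it does not depend on the windows.

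**2. The two tables compared by drug and route.**

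| Drug and route | Conversion factor (7a) | Window (4a) |
|---|---|---|
| Meperidine IV, SC, PO | yes | none |
| Ketobemidone PO, IV | yes | none |
| Duramorph IT | yes | none |
| Morphine IM | yes | none (IV, PO, SC only) |
| Tramadol IM | yes | none (PO only) |
| Oxycodone IM, SC | none (PO, IV only) | 6 h |

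The conversion table holds 23 drug-route pairs, of which 3 + 2 + 1 + 1 + 1 = 8 have no window. If Duramorph IT is never given as rescue, 7 of 22 remain. For the row "Ultram, Tramadol, Tramadol hydrochloride", which appears in both tables, only the IM route is uncovered; the same is true of morphine.

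**3. Effect on one patient.** I used time differences in the trapezoidal rule; the formula printed in 7a adds the times, which is a separate matter. Changing one interior score by Δ changes the AUC by Δ × (gap before + gap after) / 2.

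*Single example (assumed values).* An unlisted opioid is given at 0.5 h with a score of 8, and the true scores at 6 h and 12 h are 3.
- 2 h or 4 h window: (8+3)/2 × 5.5 + (3+3)/2 × 6 = 30.25 + 18 = 48.25.
- 6 h window: (8+8)/2 × 5.5 + (8+3)/2 × 6 = 44 + 33 = 77.0.
- Difference: 28.75 units for this patient.

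*Averaged over random dose times (assumed pre-dose score 7, scheduled scores 3, 6-hourly assessments).* With one dose, a 6 h window always catches one scheduled score and a 2 h window does so one time in three. Where they differ, the mean gap from dose to score is 4 h. The average difference is 2/3 × 4 × (4 + 6)/2 = 13.3 units. Simulation gives the same 13.3 for one dose, 22.6 for two doses and 32.7 for four.

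**4. Effect on an arm mean.** The margin of 38 applies to the difference in mean AUC. In an arm of 50, the patient in the single example moves the mean by 28.75/50 = 0.575 units, and 0.575/38 = 1.5% of the margin. The averaged cases give 13.3/50 = 0.27 to 32.7/50 = 0.65 units per affected patient.

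If a fraction f of one arm only is affected, the shift is f × 13.3 (one dose) to f × 32.7 (four doses):

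| f | Shift in arm mean | Share of 38 |
|---|---|---|
| 5% | 0.7 to 1.6 | 2% to 4% |
| 10% | 1.3 to 3.3 | 4% to 9% |
| 30% | 4.0 to 9.8 | 11% to 26% |

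Equal use in both arms would largely cancel in the difference.

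**The case against.** The strongest reply has four parts.

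- **The window belongs to the drug, not the arm.** Whatever length is chosen applies to both groups. Bias needs unequal use of that drug and a choice influenced by the data. This stands, and it is why the rule could bias the comparison but cannot be said to do so. The documents permit an unblinded choice; they do not say that one will be made.
- **Unlisted use may be rare.** Section 7a says the opioid analysis follows an approach from earlier studies, so a long conversion list does not prove that these drugs are expected on this pathway. This also stands. Still, the plan itself names the drugs, so their windows can be fixed now.
- **The note concerns unlisted medications.** Morphine and tramadol are listed, and only the IM route is missing, so the post-hoc rule may not reach them. That is fair, but it would leave those doses with no rule at all.
- **Some mismatches are only naming.** Oxycontin is grouped with oxycodone in the window table, and plain hydrocodone sits beside a combination product that has a factor. These need a word of clarification only.

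A reader might infer two stronger claims. One is that a single dose can use up most of the margin, because 28.75 lies near 38. That sets one patient's shift against a margin for arm means. The other is that intrathecal Duramorph distorts the opioid co-primary. Duramorph has a conversion factor, the window plays no part in the opioid total, neither arm as described in section 4a includes it, and nothing says it is given as rescue.

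**Conclusion.** The point holds as a fault of pre-specification. Part of the derivation of an unblinded co-primary is left open until after arm-level data can be seen, for drugs that the plan already lists. It could bias the pain AUC comparison if use of those drugs differs by arm. The effect is probably small: about 0.3 to 0.7 units of an arm mean per affected patient in these illustrations, and about 2% to 9% of the margin if 5% to 10% of one arm is affected. It would become material only with much heavier, one-sided use, such as the 30% row.

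These sizes rest on the assumed scores, dose times and frequencies, and on a comparison of the extreme windows of 2 h and 6 h. The documents give no frequency of unlisted-opioid use. The sample size is unaffected. The opioid co-primary is touched only by the missing factor for oxycodone IM and SC.

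**What to change.** Before the 20-per-group interim, and by someone blind to arm:

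1. Replace the post-hoc rule with windows fixed in writing, used unchanged at the interim and final analyses.
2. Align the two tables row by row. Where only a route is missing, carry over the same drug's existing window: 4 h for morphine (all its listed routes) and 6 h for tramadol. Set a window for meperidine and ketobemidone. For Duramorph IT, set one or state that it does not count as rescue.
3. Give every opioid dose a conversion value, including oxycodone IM and SC, and clarify where Oxycontin and plain hydrocodone belong.
4. Pre-specify one default window within the table's 2 to 6 h range for any opioid still unlisted. Six of the nine window rows use 6 h, so that is the value with most support in the table. Repeat the AUC analysis with the default at the other table values.

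The cost is a few table rows and a short sensitivity analysis. The downside is that a fixed default may suit an unforeseen drug less well than a tailored window. These are scoring rules only and change no patient's treatment.

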The study is powered for the primary outcome of Area under the Curve (AUC) for pain from 0-48 hours. From review of the literature of previous studies, we deemed a margin of 80% of 48 hours to be non-inferior [24,25,]. A group sample size of 50 per cohort is needed achieve a 90% power to detect non-inferiority using a one-sided, Mann-Whitney test. The margin of non-inferiority is 38 (80% of 48 hours). The non-inferiority margin corresponds to an increase in pain, not a decrease. The pain VAS ranges from 0 to 10, with 10 being the worst pain. Therefore, non-inferiority will be declared if the average AUC for liposomal bupivacaine is no more than 38 units compared to the average AUC in the TEA group. The true difference between the means is assumed to be 0.0. The significance level (alpha) of the test is 0.025 and the data are drawn from populations with standard deviations of 55.0. These assumptions were derived from previous Pacira studies. It is reasonable to assume that the standard deviation of the AUC for 0-48 hours is about 55 units and the difference between the groups is 0. Sample size calculations were performed using PASS (PASS 16 Power Analysis and Sample Size Software (2018). NCSS, LLC. Kaysville, Utah, USA, ncss.com/software/pass). Of note, with sequential testing of the co-primary endpoints, the study remains to be adequately powered with the addition of the total opioid consumption co-primary endpoint. A sample size of 50 participants in each arm will have adequate power (>90%) to detect non-inferiority with a margin of 21.2 IV morphine equivalents using a one-sided test with a common standard deviation of 25 and alpha of 0.025. The non-inferiority margin was determined by the clinically significant threshold of 10.6 mg in daily IV morphine equivalent dose [24], therefore, 21.2 morphine equivalent dose for over 2 days (0-48 hours).

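### The AUC formula in section 7a, as shown, adds consecutive assessment times where the trapezoidal rule it cites subtracts them; coded literally, the result is not an area and cannot be set against the margin of 38

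*Combined protocol and SAP*

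**What the plan says.** Section 7a (Study Statistics, primary outcome variables) states: "The area under the curve (AUC) is derived using the trapezoidal rule (see formula below) using the adjusted and imputed VAS pain scores". The formula that follows is "AUC = \left\{ \sum_{i=2}^n (p_i + p_{(i-1)})(t_i + t_{(i-1)}) \right\} / 2". No other section gives a different or corrected formula.

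On which scores enter, the same paragraph says "AUC will start with the first postsurgical pain assessment" and "All pain assessments through 48 hours after surgery, including both scheduled and unscheduled will be used in deriving AUC", with exact times. Section 4a sets the pain schedule "at rest at 6, 12, 18, 24, 30, 36, 42, 48, and 72 hours after surgery" and adds: "Subjects will also record an unscheduled pain score immediately before any requested opioid pain medication". The number of points therefore differs between patients and depends on opioid requests.

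The sample-size text in section 7a states: "The margin of non-inferiority is 38 (80% of 48 hours", with an SD of 55 and a pain scale of 0 to 10. Section 4a has the interim comparison at 20 patients per group use the average AUC over 0 to 48 hours.

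**The concern.** The trapezoidal rule takes the mean of two neighbouring scores times the interval between them. With the sum of the two times in place of the interval, the expression is no longer an area. It depends on where the clock starts, gives later scores more weight, and depends on how many scores were recorded as well as on how high they were.

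This is the only operational definition of an endpoint on which the trial must succeed, because section 7a requires significance on both co-primary endpoints. The same AUC is used at the interim look. If the formula were programmed as shown, the non-inferiority comparison would set a quantity on one scale against a margin on another. Because unscheduled scores are triggered by opioid requests, the pain endpoint would also partly count those requests and so blur into the second co-primary endpoint.

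**Working it through.** **Inputs.** Scheduled times within the window: 6, 12, 18, 24, 30, 36, 42 and 48 h (section 4a). Margin 38, SD 55, true difference 0, one-sided alpha 0.025, power 90%, Mann-Whitney test, 50 per arm (section 7a). Pilot mean pain 3.9 and 4.0 (section 7b). The pain level of 4 used below is taken from the pilot.

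**The plan's own figures.** The margin: 0.8 × 48 = 38.4, stated as 38. The sample size by normal approximation: 2 × (55 × (1.960 + 1.282) / 38)² = 44.02, so 45 per arm. The noncentral t needs 46. Allowing for the Mann-Whitney test, 46 × π/3 = 48.2, so 49. At 50 per arm the Mann-Whitney power is about 0.916. The stated 50 for 90% power is reproduced.

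**Constant pain p at the scheduled times.**
- Formula as shown: p × (18 + 30 + 42 + 54 + 66 + 78 + 90) = 378p. For p = 4 this is 1512.
- Trapezoidal rule: p × 7 × 6 = 42p. For p = 4 this is 168, smaller by a factor of 9.

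**Weight of single scores.** An interior score has coefficient (t_before + 2t + t_after)/2 in the formula as shown. That is (6 + 24 + 18)/2 = 24 at 12 h and (36 + 84 + 48)/2 = 84 at 42 h, or 3.5 times as much. The trapezoidal rule gives each of them 6.

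**Clock origin.** Counting time from 10 h earlier adds 20 to each of seven time sums, so the value for p = 4 rises by 4 × 140 = 560 to 2072. The area stays at 168.

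**Extra scores with pain unchanged at 4.** Between two existing scores, an extra score at time t adds 2t × p to the formula as shown and nothing to the area.

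| Extra scores of 4 | Formula as shown | Area |
|---|---|---|
| none | 1512 | 168 |
| 9 h | 1584 | 168 |
| 20 h | 1672 (+160) | 168 |
| 45 h | 1872 | 168 |
| 9, 20, 33 and 45 h | 2368 | 168 |

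The worst-observation replacement in rescue windows changes nothing here, because under constant pain the worst score is also 4.

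**The rise is not universal.** Take 8 at 24 h and 2 at 30 h: 10 × 54 / 2 = 270. Insert 0 at 27 h: 8 × 51 / 2 + 2 × 57 / 2 = 204 + 57 = 261, a fall of 9.

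**Scale of the margin and SD.** For a constant difference in pain over the eight scheduled scores:
- Margin: 38/42 = 0.90 points on the area scale (38/48 = 0.79 if the curve ran from 0 h); 38/378 = 0.10 points on the scale of the formula as shown.
- SD: 55/42 = 1.31 points (55/48 = 1.15) on the area scale; 55/378 = 0.15 points on the other.
- Pilot difference of 0.1 points: 4.2 units on the area scale; 37.8 units on the other, almost the whole margin.

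Only the area scale fits a margin built as 80% of 48 hours.

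**The case against.** The strongest reply is that this is one character in a displayed equation converted from PDF, and that the intent is plain. The plan calls the endpoint an area, names the rule, asks for exact times, and says the approach follows previous studies by the manufacturer. A statistician who programs the named rule will use time differences, and a value such as 1512 would be noticed at once because the largest possible area is 10 × 48 = 480.

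Much of this stands. The text alone cannot rule out a reading fault, although the minus signs in the formula's own subscripts survived, which makes one less likely. The intent is not in doubt, and nothing in the documents shows that any analysis used the plus sign. What remains is that the only formula given contradicts the rule it is meant to express. A programmer must depart from one or the other, in a trial where investigators and participants are not blinded.

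Three stronger readings are tempting, and the documents do not support them:
- A reader might infer that the value rises with every added score, or that patients who request more opioid score higher whatever their pain. The counterexample shows otherwise: the change depends on the added score and its neighbours, and scores of zero throughout give zero. A rise is the usual case, since a score taken just before an opioid request is unlikely to be very low.
- A reader might infer that the trial is wrongly sized. It is not: the margin and SD are already on the area scale, and 50 per arm is reproduced.
- A reader might take the factor of 9 or the 0.10 points as the expected distortion of the trial result. They illustrate literal use of the formula under constant pain with scheduled scores only.

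**Conclusion.** The concern holds for the formula as it appears in the text: it contradicts the trapezoidal rule named in the same paragraph and is wrong as written. Followed literally, it yields no area and nothing that can be compared with the margin of 38 or the SD of 55. The size is large where it can be computed exactly: 1512 against 168 for constant pain of 4, and 160 units, over four times the margin, for a single extra unchanged score at 20 h.

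The conclusion is conditional on two things: that the plus sign is on the source page, and that someone codes the formula as printed. Sample size, alpha, margin and SD stand as they are. Because this formula defines a co-primary endpoint, it should be settled before any AUC is computed, including at the interim look.

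**What to change.** Check the source page. If the plus sign is there, correct the formula in section 7a to

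`AUC = { sum over i = 2..n of (p_i + p_(i-1)) × (t_i - t_(i-1)) } / 2`

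and confirm that the interim and final programs use the time difference. A simple test: constant scores of 4 at 6, 12, ..., 48 h must return 168, and still 168 after an extra 4 is inserted at 20 h.

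The cost is a one-sign correction and a short program check. Design, data collection, margin and sample size do not change. If the source page already shows a minus sign, only the program check remains.

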All participants will otherwise be enrolled on the standard gyn-oncology ERAS pathway which includes pre-operative education, pre-operative medications, post-operative medications, post-operative fluid management, and mobility and feeding protocols.

Participation will be offered to patients undergoing a planned laparotomy via midline vertical skin incision on the gynecologic oncology service. Patients will be identified from gynecologic oncology pre-operative clinics. Eligible participants will be stratified based on pre-operative likelihood of malignancy (into likely benign disease vs. likely malignant disease). This stratification will be based upon the surgeon's preoperative impression of likelihood of malignancy. Participants will then be randomized 1:1 via a stratified randomized technique that accounts for a binary (yes/no) likelihood of malignancy by the inpatient pharmacy within 48 hours of surgery to the two study arms. Consent for study participation will be reviewed with the patient and signed prior to surgery.

In the rare event a patient enrolled on trial does not proceed with surgery, their slot will not be reallocated in the randomization scheme. Specifically, the inpatient pharmacy will generate random treatment assignments as follows:

1. IDS has randomization list from statistician
2. Randomization is stratified by "suspicion of cancer – Yes or No"
3. Study team will complete Randomization Request form prior to date of surgery and fax to IDS
4. If randomized to liposomal bupivacaine arm,
 - a. The authorized prescriber will enter Epic order (which will be modified to reflect the new IRB number)
 - b. At time of surgery an OR staff member will call IDS to coordinate pickup/delivery of study drug
5. If randomized to TEA arm,
 - a. The study team will notify the anesthesia block team the day before surgery to put the patient on the block list as per existing clinical work-flow for patients planned for pre-procedure blocks.

All participants will be enrolled on the standard gyn-oncology ERAS pathway which includes pre-operative education, pre-operative medications, post-operative medications, post-operative fluid management, and mobility and feeding protocols.

Patients will be considered to be “on study” until collection of VAS pain scores and opioid consumption is complete on postoperative day 14. Each participating individual will have no extra or additional outpatient study visits.

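### Randomisation is stratified by suspicion of malignancy, but neither co-primary model pre-specifies the stratum, and further covariates are left open with no list or time of choice

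*Combined protocol and SAP*

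**What the plan says.** **Randomisation (Section 4a).** "Participants will then be randomized 1:1 via a stratified randomized technique that accounts for a binary (yes/no) likelihood of malignancy". The pharmacy works from a prepared list ("IDS has randomization list from statistician"). No blocking or other method of balancing within strata is described.

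**Pain AUC (Section 7a).** "The AUC for VAS may be analyzed using ANOVA with treatment group as a main effect and include other covariates as deemed reasonable". The decision rests on that model: the 95% interval for the difference between "treatment groups and the one-sided test performed at 2.5% level of significance will be inspected for non-inferiority".

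**Opioid total (Section 7a).** The 48-hour total "may be analyzed using ANCOVA with treatment group as a main effect and include other covariates as deemed reasonable", with the same decision rule. The scale is also open: "The data may be natural log transformed".

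**Sample size (Section 7a).** "A group sample size of 50 per cohort is needed achieve a 90% power to detect non-inferiority using a one-sided, Mann-Whitney test". The inputs are a margin of 38, SD 55, a true difference of 0 and one-sided alpha 0.025. For opioids they are a margin of 21.2 mg, SD 25 and the same alpha, with power stated as above 90%.

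**Setting.** Patients and investigators know the allocation (Sections 4a and 4c). The average AUC is compared between arms at an interim analysis with 20 patients per group (Sections 4a and 7b).

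**The concern.** Treatment is the only term that either model must contain. Two consequences follow, and they differ in kind.

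First, stratified allocation that balances the arms on a prognostic factor removes that factor's contribution from the variability of the treatment difference. A model without the factor still counts it as residual error. The reported standard error is then larger than the true one, and the upper limit compared with 38 or 21.2 sits further out than the design requires.

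Second, the plan does not say which covariates may enter, how they are selected or when. A treatment-only model, a model with the stratum, and a model with several other baseline variables all comply with it. Section 7a states that type I error is held at 0.025 across the two non-inferiority tests. That holds for a model fixed in advance. It need not hold for one selected from several after outcomes are known, in a trial where allocation is visible and an interim comparison takes place.

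**Working it through.** **1. The plan's sample size.** For a comparison of means, n per arm = 2(1.960 + 1.282)² × 55² / 38² = 44.02, so 45 (46 with the t distribution). Dividing by the Mann-Whitney efficiency under normality, 3/π = 0.955, gives 48 or 49. The stated 50 is therefore reproduced to within 2 patients.

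At 50 per arm, SE = 55 × √(2/50) = 11.0 and power = Φ(38/11.0 − 1.96) = Φ(1.495) = 93.2%. It is 92.8% by noncentral t and about 92.2% for Mann-Whitney with normal data. For opioids, SE = 25 × 0.2 = 5.0 and power = Φ(21.2/5.0 − 1.96) = Φ(2.28) = 98.9%. Both agree with the stated figures.

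**2. Omitting the stratum.** Let R² be the share of outcome variance that the stratum explains. The documents do not give it, so 0 to 20% is an assumed range. Allocation is taken as balanced within strata.

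- Reported SE without the stratum: 11.0. True SE: 11.0 × √(1 − R²).
- One-sided error of the treatment-only test: 1 − Φ(1.96/√(1 − R²)).
- Power, treatment only: Φ((38 − 1.96 × 11.0)/true SE).
- Power, stratum included: Φ(38/true SE − 1.96).

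| R² | True SE | One-sided error, stratum omitted | Power, omitted | Power, included |
|---|---|---|---|---|
| 0 | 11.00 | 2.5% | 93.25% | 93.25% |
| 5% | 10.72 | 2.2% | 93.74% | 94.34% |
| 10% | 10.44 | 1.9% | 94.24% | 95.37% |
| 20% | 9.84 | 1.4% | 95.26% | 97.14% |

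The reported SE is too large by about 3%, 5% and 12%. The power given up is 0.60, 1.13 and 1.88 percentage points. For opioids the corresponding powers are 99.0% against 99.2%, 99.2% against 99.4%, and 99.5% against 99.7%.

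To give R² a scale: with equal-sized strata the gap in mean AUC between them is 2 × 55 × √R², which is 24.6, 34.8 and 49.2 units. The 20% row therefore needs a difference between strata larger than the margin of 38.

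A simulation at the margin (20,000 runs, assumed blocks of 4, stratum prevalence 50% or 70%) gave one-sided error of 0.019 to 0.020 at R² = 10% and 0.014 at 20% with the stratum omitted, and about 0.025 with it included.

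**3. Open covariate choice.** The documents give no number of candidate covariates, so this is only an illustration of the worst case. Suppose success is declared if any subset of k optional covariates, each explaining 3 to 5% of variance, meets the AUC margin. In 4,000 runs per setting, one-sided error was about 0.032 to 0.036 (k = 2), 0.044 to 0.057 (k = 4) and 0.067 to 0.081 (k = 6). The fixed model in the same runs gave 0.022 to 0.028. These are errors for one endpoint. Requiring both endpoints to succeed lowers the joint error when both lie at their margins, but gives no relief when one is clearly non-inferior.

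**The case against.** The strongest reply is that the plan does not exclude the stratum. The wording lets other covariates in, and the randomisation factor is the obvious candidate. That is correct: a reader might infer that the models leave the stratum out, but the documents support only that it is not pre-specified.

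A reader might also infer that the standard errors will be wrong. That needs a stratum that predicts 48-hour pain or opioid use and a list balanced within strata. The stratum is the surgeon's preoperative impression of malignancy. Nothing in the documents says that it is prognostic, and no blocking is described. At R² = 0 the standard error is correct.

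Where the error does arise, it makes a false claim of non-inferiority less likely. The loss is also easy to overstate by setting adjusted power at R² above zero against the 92.8% or 93.2% that applies at R² = 0. The treatment-only test also gains power when a prognostic stratum is balanced, so the two must be compared at the same R².

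Sizing on Mann-Whitney and analysing by ANOVA does no harm to the sample size, since 50 per arm covers both. It does leave the primary method unclear.

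Finally, no passage schedules the choice of covariates after results are seen; that possibility follows from silence. The silence still matters, because nothing in the plan prevents a late choice.

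**Conclusion.** The point holds as a gap in pre-specification. The co-primary models do not name the factor used in randomisation, and further covariates are unrestricted in an open-label trial.

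The stratum part is a small efficiency loss in the conservative direction: one-sided error of about 2.2%, 1.9% or 1.4% and 0.6 to 1.9 points of AUC power at an assumed R² of 5%, 10% or 20%, given balance within strata and normal outcomes. Power exceeds 90% in every case examined and the sample size is unaffected, so the documents do not support reading the trial as underpowered.

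The covariate part bears on validity: the stated 0.025 is not guaranteed if the model is chosen after outcomes are seen. Its size cannot be fixed from the documents, and the simulated figures mark a worst case under assumed covariates.

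A reader might extend the point to the secondary outcomes. That does not fit Section 7a as written: apart from Poisson regression for length of stay, the tests named there (t, Mann-Whitney, log-rank, chi-square) have no covariate term.

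This is a free improvement.

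**What to change.** For both co-primaries, replace the permissive sentences in Section 7a with one statement: the primary analysis is a linear model with treatment and randomisation stratum (suspicion of cancer, yes or no) as fixed effects; any further baseline covariates are listed by name; and the specification is locked before the interim analysis. Non-inferiority is then read from that model's upper 95% limit. Label any other covariate model, and any Mann-Whitney analysis, as sensitivity. No change to the secondary tests is asked for here.

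The optional log transformation of the opioid total is a separate open choice that this change does not settle.

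The cost is a short SAP edit and one degree of freedom per model, with no change to sample size, margins or conduct.
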